8. Vital signs are to be measured pre- and post-dose on days of injection (Day 1 and Day 29). When applicable, vital signs should be measured before blood collection. Participants who are febrile (body temperature $\geq 38.0^{\circ}\text{C}/\geq 100.4^{\circ}\text{F}$) before injection on Day 1, or Day 29 must have the visit rescheduled within the relevant visit window to receive the injection. Afebrile participants with minor illnesses can be enrolled at the discretion of the investigator.
9. The pregnancy test at Screening and Day 1 and before the second study injection will be a point-of-care urine test. At the discretion of the investigator, a pregnancy test either via blood or point-of-care urine test can be performed at any time.
10. Samples for safety laboratory assessments (serum creatinine, urine protein, and UPCR for kidney transplant recipients only; ALT, AST, ALP, and bilirubin for liver transplant recipients only) must be collected prior to dosing on Day 1 and Day 29.
11. After Day 57, the investigator will review standard-of-care kidney and liver laboratory assessments and report any laboratory-related AEs and suspected or confirmed events of organ transplant rejection until the EOS.
12. Samples for immunogenicity (bAb against SARS-CoV-2 spike protein and neutralizing antibody against SARS-CoV-2) and assessment of SARS-CoV-2 bAb against the nonvaccine antigen (nucleocapsid protein) must be collected prior to dosing on Day 1, and Day 29.
13. For assessment of cellular immune response, blood samples will be collected on Day 1 (prior to dosing) and Day 36. Note that 20 healthy participants receiving 2-dose regimen will also have blood samples collected at Day 1 (prior to dosing) and Day 36.
14. The NP swab sample will be collected prior to dosing and used to ascertain the presence of SARS-CoV-2 via RT-PCR.

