4. Vital signs are to be collected pre- and post-dosing (participant will be seated for at least 5 minutes before all measurements are taken per [Section 7.1.4](#)) on the day of injection (BD-D1). Participants who are febrile (body temperature $\geq 38.0^{\circ}\text{C}/100.4^{\circ}\text{F}$) before dosing (BD-D1) must be rescheduled to receive the injection. Afebrile participants with minor illnesses can be vaccinated at the discretion of the investigator.
5. The pregnancy test at the BD-1 visit will be a point-of-care urine test. At the discretion of the investigator, a pregnancy test either via blood or point-of-care urine test can be performed.
6. Samples for immunogenicity (bAb against SARS-CoV-2 spike protein and neutralizing antibody against SARS-CoV-2) and assessment of SARS-CoV-2 bAb against the nonvaccine antigen (nucleocapsid protein) must be collected prior to dosing on BD-D1.
7. For assessment of cellular immune response, blood samples will be collected on Day 1 (prior to dosing), and Day 8 from previously vaccinated SOT recipients (kidney or liver).
8. All participants who chose to receive a BD. Serum sample from two ~ 4 mL blood draws. Biomarker plasma and biomarker serum samples will be stored for potential future biomarker assessment.
9. Samples for safety laboratory assessments (serum creatinine, urine protein, and UPCR for kidney transplant recipients only; ALT, AST, ALP, and bilirubin for liver transplant recipients only) must be collected prior to dosing on BD-D1.
10. After BD-D29, the investigator will review standard-of-care kidney and liver laboratory assessments and report any laboratory-related AEs and suspected or confirmed events of organ transplant rejection until the EOS.
11. Post-dosing, participants will have a 30-minute observation period.

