## 6. Statistical Analysis

### 6.1. General Considerations

The schedule of assessments is provided in Appendix 1 of Protocol Amendment 4.

**Continuous variables** will be summarized using the following descriptive summary statistics: the number of subjects (n), mean, standard deviation (SD), median, minimum (min), and maximum (max).

Confidential

**Categorical variables** will be summarized using counts and percentages.

**Baseline value**, unless otherwise specified, is defined as the most recent non-missing measurement (scheduled or unscheduled) collected before the first dose of IP.

**Pre-booster baseline value** is defined as the most recent non-missing measurement (scheduled or unscheduled) collected before the BD on BD-Day 1.

For the summary statistics of all numerical variables unless otherwise specified, the display precision will follow programming standards. See [Appendix A](#) for variable display standards.

When count data are presented, the percentage will not be displayed when the count is zero in order to draw attention to the non-zero counts. A row denoted “Missing” will be included in count tabulations where specified on the shells to account for dropouts and missing values. The denominator for all percentages will be the number of subjects in the specified group within the analysis set of interest, unless otherwise specified.

**Baseline SARS-CoV-2 status** is determined by using virologic and serologic evidence of SARS-CoV-2 infection on or before Day 1.

Positive SARS-CoV-2 status at Baseline is defined as a positive RT-PCR test for SARS-CoV-2, and/or a positive serology test based on bAb specific to SARS-CoV-2 nucleocapsid (as measured by Roche Elecsys Anti-SARS-CoV-2 assay) on or before Day 1.

Negative status at Baseline is defined as a negative RT-PCR test for SARS-CoV-2 and a negative serology test based on bAb specific to SARS-CoV-2 nucleocapsid (as measured by Roche Elecsys Anti-SARS-CoV-2 assay) on or before Day 1.

**Pre-booster SARS-CoV-2 status**, is determined by using virologic and serologic evidence of SARS-CoV-2 infection prior to the BD in Part B.

Positive pre-booster SARS-CoV-2 status is defined as a positive RT-PCR test for SARS-CoV-2, and/or a positive serology test based on bAb specific to SARS-CoV-2 nucleocapsid (as measured by Roche Elecsys Anti-SARS-CoV-2 assay) on or before the date of BD (BD-Day 1).

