- Imputation rules for missing AE dates are provided in [Appendix C](#).
- For laboratory assessments, if the majority of results are indefinite, imputation of these values will be considered. If the laboratory results are reported as below the LLOQ (e.g., <0.1), the numeric values will be imputed by  $0.5 \times \text{LLOQ}$  in the summary. If the laboratory results are reported as greater than the ULOQ (e.g., >3000), the numeric values will be imputed by ULOQ in the summary.
- For immunogenicity assessments, imputation of missing results will be considered based on description in [Section 6.4](#).
- Other incomplete/missing data will not be imputed, unless specified otherwise.

**Participant groups** will be summarized according to the schema below.

- Transplant status:
  - SOT Kidney
  - SOT Liver
  - SOT Total
  - 2-Dose Healthy
- Dosing regimens:
  - Overall
  - Unvaccinated SOTs Who Received 2 Doses
  - Unvaccinated SOTs Who Received 3 Doses
  - Previously Vaccinated SOTs Who Received a Third Dose
  - Total SOTs Who Received 3 Doses
  - Primary Series All SOTs Who Received a Booster Dose
- Primary Series All SOTs Who Received a Booster Dose:
  - Overall
  - 3-Dose Moderna
  - 3-Dose Pfizer

Confidential

- Other

Unless otherwise mentioned, the results of the analyses will be summarized according to the participant groups above. Subjects under the same dosing regimen may be combined for analyses regardless of BD. Participants that received booster may be analyzed separately from participants that did not receive booster.

**Subgroup analyses** for safety and immunogenicity endpoints may be analyzed in select subgroups specified below as applicable:

- Age (18 to < 65,  $\geq$  65)
- Time of post-transplantation (< 2,  $\geq$  2 years)
- Baseline SARS-CoV-2 Status in each part (Positive, Negative) (for safety data)
- Sex (Male, Female)
- Race (White, Communities of color)
- Anti-metabolite immunosuppression (Yes, No)
- Combination of immunosuppressants (Mycophenolate, Tacrolimus, and Prednisone; Mycophenolate and Tacrolimus; Tacrolimus; and Other)
- Previous induction therapy (Basiliximab or other monoclonal antibody; Basiliximab or other monoclonal antibody with steroids; Thymoglobulin; Thymoglobulin with steroids; or steroids alone)

All analyses will be conducted using SAS Version 9.4 or higher.

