### **6.3.3. Clinical Laboratory Results**

Clinical laboratory samples will be collected at the Day 1 visit and at post-baseline visits through the Day 57 visit for participants receiving 2 doses of IP, or through Day 113 visit for participants receiving 3 doses of IP, or through Day 29 visit for SOT participants that are previously vaccinated with Moderna COVID-19 vaccines. For participants that continue to Part B of the study and receive BD, clinical laboratory samples will be collected at BD-Day 1, BD-Day 8, and BD-Day 29. Results will be summarized using descriptive statistics at each visit by participant group and will be presented in a data listing for the Safety Set.

Using the Toxicity Grading Scale for Healthy Adult and Adolescent Volunteers Enrolled in Preventative Vaccine Clinical Trials (DHHS 2007), as described in [Table 5](#), the number and percentage of participants experiencing clinical laboratory abnormalities and changes from baseline values at each visit will be summarized by severity grade and participant group. Similarly, clinical laboratory toxicity will be summarized as the maximum over all post-injection visits. Clinical laboratory results and their toxicity grades will also be listed for the Safety Set.

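### SAP 6.3.3 gives no test-specific denominator, so under the SAP 6.1 default the percentages with graded creatinine or liver-test abnormalities are understated in any column that pools kidney and liver recipients

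*SAP*

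**What the plan says.** **Who is tested.** The schedules of events in Protocol Appendix 1 make safety laboratory sampling organ-specific. Table 7, footnote 10, lists "serum creatinine, urine protein, and UPCR for kidney transplant recipients only; ALT, AST, ALP, and bilirubin for liver transplant recipients only". Tables 8 and 9 carry the same restriction, and so does Table 10 for the booster phase. Healthy participants have neither set of tests.

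**What is reported.** For each participant group in the Safety Set, SAP 6.3.3 plans this table: "number and percentage of participants experiencing clinical laboratory abnormalities and changes from baseline values at each visit will be summarized by severity grade". It adds: "Similarly, clinical laboratory toxicity will be summarized as the maximum over all post-injection visits". SAP Table 5 (Appendix F) supplies grades for creatinine, ALP, ALT and AST, and bilirubin.

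**Which denominator.** SAP 6.1 sets a general rule: "The denominator for all percentages will be the number of subjects in the specified group within the analysis set of interest, unless otherwise specified". SAP 6.3.3 specifies nothing else.

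**Which columns.** SAP 6.1 lists participant groups by transplant status (SOT Kidney, SOT Liver, SOT Total, 2-Dose Healthy), by dosing regimen (Overall, groups such as "Unvaccinated SOTs Who Received 3 Doses", Total SOTs, and the booster group), and by primary series among booster recipients. No regimen or booster group is defined by organ. Protocol 5.2 states that enrollment is not stratified, so these groups can contain both organs.

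**The concern.** Taken together, these provisions treat a participant who was not tested as one without an abnormality. In a pooled column, liver recipients enter the creatinine denominator and kidney recipients enter the denominators for ALT, AST, ALP and bilirubin. Neither can ever contribute a case. The error therefore has one direction, downward.

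The tests matter because change in kidney and liver function is a secondary endpoint in Part A (SAP 3.2.3) and an exploratory endpoint in Part B (SAP 3.3). Protocol 7.1.3 says the tests are there to help monitor for rejection. A reader who wants to describe two doses, three doses or the booster will look at the regimen and booster columns. Two such columns with the same true rate but different organ mixes would print different percentages.

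Nothing in the SAP text would alert a programmer. SAP 3.2.3 lists the kidney and liver tests for SOT recipients without the organ restriction, which appears only in the protocol's schedule footnotes. Elsewhere the SAP does limit denominators to those with data: the Solicited Safety Sets in SAP 5.4 require that the participant contributed solicited data after the injection in question. SAP 6.3.3 has no counterpart.

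**Working it through.** **The plan's own figure.** The documents give no expected rate or precision for laboratory abnormalities. The only probability in the sample-size section concerns biopsy-proven rejection: 200 SOT participants and a true rate of 3% give 1 − 0.97^200 = 0.9977, which agrees with the stated >95%. It does not bear on the laboratory denominator.

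**Inputs**
- Planned numbers: 220 SOT recipients and 20 healthy participants, 240 in all (SAP 4.1).
- Tested for creatinine: kidney recipients only. Tested for ALT, AST, ALP and bilirubin: liver recipients only (Protocol Appendix 1).
- Denominator: everyone in the column within the Safety Set (SAP 6.1, SAP 6.3.3).
- Kidney-to-liver mix: an assumption. The Amendment 2 history (Protocol 10.6.2) mentions a site projection of 2:1, which is not a quota. The range shown is 1:1 to 4:1.
- True rate among those tested: an assumption, 10% for illustration.

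**Formula.** Displayed percentage = true rate among those tested × (number tested ÷ number in column).

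**SOT Total, N = 220**

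| Kidney : liver | Kidney n / liver n | Factor, creatinine | Factor, liver tests | True 10%: creatinine shown | True 10%: liver test shown |
|---|---|---|---|---|---|
| 1:1 | 110 / 110 | 0.50 | 0.50 | 5.0% | 5.0% |
| 2:1 | 147 / 73 | 0.67 | 0.33 | 6.7% | 3.3% |
| 4:1 | 176 / 44 | 0.80 | 0.20 | 8.0% | 2.0% |

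Example at 2:1: 10% × 147/220 = 6.7% for creatinine, and 10% × 73/220 = 3.3% for a liver test.

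**A column of all 240, if the 20 untested healthy participants are included**

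| Kidney : liver | Factor, creatinine | Factor, liver tests | True 10%: creatinine shown | True 10%: liver test shown |
|---|---|---|---|---|
| 1:1 | 0.46 | 0.46 | 4.6% | 4.6% |
| 2:1 | 0.61 | 0.30 | 6.1% | 3.0% |
| 4:1 | 0.73 | 0.18 | 7.3% | 1.8% |

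**Effect of mix alone.** Take two regimen columns, each with a true 10% rate of raised ALT among liver recipients. One enrolled at 1:1 prints 5.0%; one enrolled at 4:1 prints 2.0%.

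**After the fix.** With participants who have a result for the test as the denominator, the factor is 1 and each row returns 10%.

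**The case against.** The strongest replies are these.

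1. **The default allows exceptions.** The SAP 6.1 rule gives way where something else is specified, and the table shells are not in the documents. Shells could set another denominator. This stands as a limit on certainty, but the SAP text itself contains no exception for laboratory tables. A Missing row, where the shells ask for one, would display the untested without removing them from the denominator.

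2. **The columns may be crossed with organ.** SAP 6.1 gives transplant status and dosing regimen as separate lists and does not say whether they are crossed. Protocol 8.3.2 asks for safety by cohort and subcohort, and Protocol 8.3.1 gives kidney and liver as examples of subcohorts. If they are crossed, each regimen would have undiluted kidney and liver columns. This stands in part: the regimen and booster groups are affected only where they are not split by organ. The pooled columns remain diluted on either layout.

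3. **Correct figures exist elsewhere.** The SOT Kidney and SOT Liver columns show own-organ rates free of organ-mix dilution. Counts are right, continuous summaries use the observed n, and SAP 6.3.3 lists all results and grades. This stands.

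4. **Patient-level monitoring does not depend on these tables.** Protocol 7.6.1 works from individual changes from baseline, repeat testing and review by the Safety Review Committee. Adjudicated biopsy-proven rejection is a primary endpoint and is summarised separately. This stands.

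A reader might infer that organ toxicity is understated in every regimen and total column, UPCR included, and that the trial would give false reassurance about graft safety. The documents do not support that. UPCR and urine protein have no grade in SAP Table 5, not every column need pool organs, and points 3 and 4 leave the signal visible by other routes.

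**Conclusion.** Wrong as written, within limits. The stated denominator rule, applied to organ-specific tests, yields percentages for graded creatinine, ALT, AST, ALP and bilirubin abnormalities that are too low in any column holding both kidney and liver recipients. Those columns are SOT Total, Overall, and the regimen and booster groups unless they are split by organ. The same holds for the by-visit tables and for the worst-grade table.

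The direction follows from the documents. The size does not, because it depends on an organ mix that the plan neither fixes nor forecasts beyond a site projection in the amendment history. Across mixes from 1:1 to 4:1, creatinine percentages in SOT Total would be multiplied by 0.50 to 0.80 and liver-test percentages by 0.50 down to 0.20. The effect on liver tests is the larger whenever kidney recipients are the majority.

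This is a reporting error in descriptive tables. It leaves the data intact, and the study plans no formal between-group comparison.

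**What to change.** Add a paragraph to SAP 6.3.3 stating that:
- creatinine, urine protein and UPCR are summarised in kidney recipients, and ALT, AST, ALP and bilirubin in liver recipients, within each regimen and booster group;
- at each visit, the denominator for a test is the participants with a non-missing result for that test at that visit;
- for the worst post-injection grade, the denominator is the participants with at least one post-injection result for that test.

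Print that denominator in each cell block, and show a test as not applicable, not as zero, in a column where it was not scheduled. The non-missing rule also prevents a missed sample from counting as a normal result in the SOT Kidney and SOT Liver columns.

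The cost is one SAP paragraph and matching table shells. No new data, visits or samples are needed.

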### **6.3.5. Vital Sign Measurements**

Vital signs will be graded using the Toxicity Grading Scale for Healthy Adult and Adolescent Volunteers Enrolled in Preventative Vaccine Clinical Trials (DHHS 2007). This grading scale is displayed in [Table 6](#).

Vital sign measurements, including systolic and diastolic blood pressures, heart rate, respiratory rate, and body temperature, and baseline height, weight, and BMI will be presented in a data listing.

The abnormalities meeting the toxicity grading criteria (Grade 2 or higher) in any vital sign measurement will be listed separately. If a subject has a vital sign result with Grade 2 or higher abnormality at any post-injection visit, then all results of vital sign measurement for that subject will be presented in the listing. The abnormal values meeting the toxicity grading criteria will be flagged in the data listing.

Observed values and changes from baseline for all vital sign measurements will be summarized at each visit by participant group as defined in [Section 6.1](#). Shift from baseline in the toxicity grades at each visit (including post-dose assessment on day of injection) and shift from baseline in the toxicity grades to the worst post-baseline result will also be summarized by participant group. Change from baseline results and shift from baseline in toxicity grades will be based on pre-booster baseline (collected prior to BD on BD-Day 1) for participants in Part B.

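### Laboratory change from baseline in Part B is measured from before the first Part A dose in Groups B2 and B3, because SAP 6.3.3 lacks the pre-booster switch that 6.3.5 makes for vital signs

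*SAP*

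**What the plan says.** SAP 6.1 defines two reference values. The ordinary baseline, "unless otherwise specified, is defined as the most recent non-missing measurement (scheduled or unscheduled) collected before the first dose of IP". The pre-booster baseline "is defined as the most recent non-missing measurement (scheduled or unscheduled) collected before the BD on BD-Day 1". No general rule says that the second replaces the first in Part B.

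SAP 6.3.3 brings Part B into the laboratory analysis: "clinical laboratory samples will be collected at BD-Day 1, BD-Day 8, and BD-Day 29". It then plans that abnormalities and "changes from baseline values at each visit will be summarized by severity grade and participant group". The word baseline is unqualified there.

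SAP 6.3.5 does qualify it. For vital signs, change from baseline and shift in toxicity grade "will be based on pre-booster baseline (collected prior to BD on BD-Day 1) for participants in Part B".

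The Part B laboratory endpoint (SAP 3.3; Protocol Table 1) is exploratory. It covers kidney and liver function from BD-Day 1 through BD-Day 29 in transplant recipients.

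**The concern.** A programmer who follows the SAP literally applies the 6.1 default to laboratory change, because 6.3.3 specifies nothing else. Section 6.3.5 supports that reading: where the authors wanted the pre-booster value for a safety measure, they said so.

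For someone who came through Part A, the tabulated change at BD-Day 29 would then cover the whole of Part A as well as the four weeks after the booster. In B2 it would span three earlier study doses and in B3 one, plus any change in immunosuppression or graft function along the way. The endpoint asks about the period after the booster. A change summary on the default baseline can show a shift that preceded the booster, or hide one that followed it.

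**Working it through.** **Inputs**
- Nominal booster day (Protocol Table 10): D205 for transplant recipients with three Part A doses (B2), D120 for those with one (B3). Window: 14 days early.
- Default baseline: Part A Day 1, before dosing (SAP 6.1).
- Group B4: the booster is the first study injection (SAP Appendix B, Table 3 footnotes), so the default and pre-booster baselines are the same value.
- Group B5: not affected. Protocol 7.1 lists Part B safety laboratory tests for B2, B3 and B4 only.

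The plan states no figure of its own here to reproduce.

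**Gap from default baseline to booster** = booster day − 1
- B2: 205 − 1 = 204 days; with the full window, 204 − 14 = 190 days.
- B3: 120 − 1 = 119 days; with the full window, 119 − 14 = 105 days.
- B4: 0 days.

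Actual gaps may be longer. The protocol requires at least 4 months from the last dose, and Part B was opened to people already in follow-up.

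**Span covered by the tabulated change** = gap + 7 (BD-Day 8) or gap + 28 (BD-Day 29), nominal days

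| Group | BD-Day 8, default | BD-Day 29, default | BD-Day 8, pre-booster | BD-Day 29, pre-booster |
|---|---|---|---|---|
| B2 | 204 + 7 = 211 | 204 + 28 = 232 | 7 | 28 |
| B3 | 119 + 7 = 126 | 119 + 28 = 147 | 7 | 28 |
| B4 | 7 | 28 | 7 | 28 |

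**Pooling.** SAP 6.1 plans a group of all transplant recipients who received a booster, with Overall, 3-Dose Moderna, 3-Dose Pfizer and Other columns. Overall would combine B2 and B3 on a months-old reference with B4 on a same-day one. B4 may include people given three Moderna doses outside the study (Protocol Table 3), so the Moderna column can mix both references too. The Pfizer column would contain B4 alone. The baseline in use would therefore vary with primary-series type.

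**Direction of error (assumed creatinine values in mg/dL, for illustration only)**
- Day 1 = 1.2, pre-booster = 1.6, BD-Day 29 = 1.6. Default change: 1.6 − 1.2 = +0.4. Pre-booster change: 1.6 − 1.6 = 0.
- Day 1 = 1.5, pre-booster = 1.2, BD-Day 29 = 1.5. Default change: 1.5 − 1.5 = 0. Pre-booster change: 1.5 − 1.2 = +0.3.

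The default can create an apparent post-booster change or conceal a real one.

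**What does not depend on baseline.** SAP Table 5 grades creatinine on absolute values and the liver tests on multiples of the upper limit of normal. Grade counts by visit and the maximum post-injection grade are the same whichever baseline is used. So are the descriptive statistics of observed values at each visit.

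**The case against.** The strongest reply is that this is a missing cross-reference and not a rule anyone chose. SAP 6.1 defines the pre-booster baseline for measurements in general, its Part B analysis period starts at the booster, Table 3 has a pre-booster BD-Day 1 laboratory visit, and the endpoint itself starts on BD-Day 1. One could argue that the endpoint wording already counts as specifying otherwise. That is a fair account of the likely intent. It does not settle the matter: neither the endpoint nor Table 3 names a reference for change, and 6.3.5 shows that the switch was written out where it was wanted.

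The reply also limits the consequences, and these limits stand:
- The Part B laboratory objective is exploratory and the study is descriptive, without formal hypothesis testing. A reader might infer that the primary Part B safety objective is undermined. Its endpoints are reactions, adverse events and biopsy-proven rejection, and none of them uses this baseline.
- Observed values at BD-Days 1, 8 and 29, and the listings, still show the course after the booster, though not the within-participant change summary.
- A reader might compare a percentage rise in creatinine with the 25% figure in Protocol 7.6.1. That figure is an investigator criterion for repeating a test. SAP 6.3.3 plans no percent-change table and applies no such cut-off, so the plan would not flag anyone on that basis.
- A reader might conclude that vital signs are the only analysis with a pre-booster reference. That is true among the safety analyses. Seroresponse (SAP 6.4.3.1) also uses a pre-booster baseline, and the Part B infection analyses use pre-booster infection status.

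**Conclusion.** The concern holds for laboratory change from baseline in Groups B2 and B3, and for any booster column that pools them with B4. As written, the reference is nominally 204 days (B2) or 119 days (B3) before the booster, or 190 and 105 days with the full early window. The BD-Day 29 change then spans 232 or 147 days where the endpoint covers 28.

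This is wrong as written and not merely unspecified, because the stated default supplies a definite reference that does not fit the endpoint. It rests on the literal reading of SAP 6.1 and on the nominal booster days. It should be corrected, but it is contained: the documents do not support extending it to severity grades, observed values, B4, B5 or any primary or secondary endpoint.

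**What to change.** Add to SAP 6.3.3 that, for participants in Part B, laboratory change from baseline (and any shift display, if one is produced) is based on the pre-booster value collected before the booster on BD-Day 1. This mirrors the wording in 6.3.5 and gives B2, B3 and B4 the same reference.

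The cost is one sentence and the matching programming specification. No new data are needed: under Protocol Table 10 the safety laboratory samples "must be collected prior to dosing on BD-D1".

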7.6.1. Safety Review Committee

An independent safety review committee (SRC) consisting of transplant nephrologist(s) and hepatologist(s) not involved in the conduct of the study will monitor and adjudicate for events of organ transplant rejection starting from Day 1 and throughout the study period. The SRC will operate under the rules of an approved charter that will be written and reviewed at the organizational meeting of the SRC. Details regarding the SRC composition, responsibilities, procedures, and frequency of data review will be defined in its charter.

In Part A, the investigator will review laboratory safety assessments of kidney and liver function performed as part of the study at Day 1, Day 8, Day 29, Day 36, and Day 57 for unvaccinated SOT recipients who receive 2 doses (Group A1) and on additional Days 85, 92, and 113 for unvaccinated SOT recipients who receive 3 doses (Group A2), and at Day 1 (dose 3), Day 8, and Day 29 for previously vaccinated SOT recipients (Group A3), for close monitoring around the time of vaccination. In Part B, the investigator will review laboratory safety assessments of kidney and liver function performed as part of the study at BD-D1, BD-D8, and BD-D29. If any of the following criteria are met, the laboratory test(s) must be repeated within 3 days: an increase in serum creatinine $\geq 25\%$ from baseline or increase in UPCR > 0.5 g/g from baseline in kidney SOT

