## 9.6. Appendix F. Severity Grading of Laboratory Abnormalities

**Table 5. Severity Grading of Laboratory Abnormalities**

Serum Chemistry a	Mild (Grade 1)	Moderate (Grade 2)	Severe (Grade 3)	Potentially Life-threatening (Grade 4) b
Creatinine (mg/dL)	1.5 – 1.7	1.8 – 2.0	2.1 – 2.5	> 2.5 or requires dialysis
ALP; increase by factor	1.1 – 2.0 × ULN	2.1 – 3.0 × ULN	3.1 – 10 × ULN	> 10 × ULN
Liver function tests – ALT and AST; increase by factor	1.1 – 2.5 × ULN	2.6 – 5.0 × ULN	5.1 – 10 × ULN	> 10 × ULN
Bilirubin – when accompanied by any increase in liver function test; increase by factor	1.1 – 1.25 × ULN	1.26 – 1.5 × ULN	1.51 – 1.75 × ULN	> 1.75 × ULN
Bilirubin – when liver function test is normal; increase by factor	1.1 – 1.5 × ULN	1.6 – 2.0 × ULN	2.0 – 3.0 × ULN	> 3.0 × ULN

Abbreviations: ALP = alkaline phosphatase; ALT = alanine aminotransferase; AST = aspartate aminotransferase; ULN = upper limit of the normal range.

- a The laboratory values provided in the tables serve as guidelines and are dependent upon institutional normal parameters. Institutional normal reference ranges should be provided to demonstrate that they are appropriate.
- b The clinical signs or symptoms associated with laboratory abnormalities might result in characterization of the laboratory abnormalities as potentially life-threatening (Grade 4). For example, a low sodium value that falls within a Grade 3 parameter (125 – 129 mEq/L) should be recorded as a Grade 4 hyponatremia event if the participant had a new seizure associated with the low sodium value.

Source: Guidance for industry – Toxicity Grading Scale for Healthy Adult and Adolescent Volunteers Enrolled in Preventive Vaccine Clinical Trials; tables for laboratory abnormalities ([DHHS 2007](#)).

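### SAP 6.3.3 reports worst laboratory grade without baseline grade and does not count the protocol's own graft-function change criteria

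*SAP*

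**What the plan says.** SAP 6.3.3 plans four outputs for the kidney and liver tests.

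- By-visit summaries: "Results will be summarized using descriptive statistics at each visit by participant group and will be presented in a data listing for the Safety Set".
- Counts and percentages of participants "experiencing clinical laboratory abnormalities and changes from baseline values at each visit will be summarized by severity grade and participant group".
- A worst-value summary: "Similarly, clinical laboratory toxicity will be summarized as the maximum over all post-injection visits".
- A listing of results with their toxicity grades.

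The grades come from SAP Table 5, which reproduces a scale for healthy volunteers. Creatinine is graded in mg/dL: 1.5 to 1.7 is Grade 1, 1.8 to 2.0 Grade 2, 2.1 to 2.5 Grade 3, and above 2.5 (or dialysis) Grade 4. ALT, AST, ALP and bilirubin are graded as multiples of ULN. Urine protein and UPCR have no row.

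For vital signs, SAP 6.3.5 goes further. It plans a shift in grade at each visit, and adds that "shift from baseline in the toxicity grades to the worst post-baseline result will also be summarized by participant group". It also fixes the Part B reference: change and shift in "toxicity grades will be based on pre-booster baseline (collected prior to BD on BD-Day 1) for participants in Part B". SAP 6.3.3 has neither provision.

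Protocol 7.6.1 sets change criteria against baseline: creatinine up by at least 25% or UPCR up by more than 0.5 g/g in kidney recipients, and ALT or AST above 3 times baseline in liver recipients. If one is met, "the laboratory test(s) must be repeated within 3 days". No SAP table counts participants who meet them.

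**The concern.** SAP 3.2.3 makes change in liver and renal function after vaccination a secondary endpoint in transplant recipients. The transplant exclusion criteria in protocol 4.1.1.2 set no creatinine limit, so recipients with stable but reduced graft function can enrol. On an absolute creatinine scale they are graded at every visit, and a worst-grade table without baseline grade shows them as post-vaccination toxicity. In the other direction, a rise large enough to call for a retest under the protocol can leave the grade where it was. The grade tables would then mix old dysfunction with new, and no planned table would state how many recipients had a change of the size that the protocol itself treats as a signal.

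**Working it through.** The SAP gives no figure on this point to reproduce. Its one safety figure (SAP 4.2, at least one rejection among 200 recipients at a true rate of 3%) checks: 1 − 0.97^200 = 0.998, consistent with more than 95%. Nothing below depends on it.

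**1. Stable values.** Inputs: the creatinine cut-points in SAP Table 5. Baselines are assumed, because the documents give no distribution. A stable 1.6 mg/dL is Grade 1 at every visit and a stable 2.6 is Grade 4, both with zero change. Any stable value of 1.5 or more is graded throughout.

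**2. A 25% creatinine rise (protocol 7.6.1).** Follow-up value = 1.25 × baseline.

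| Assumed baseline (mg/dL) | Grade | 1.25 × baseline | Grade |
|---|---|---|---|
| 1.0 | none | 1.25 | none |
| 1.1 | none | 1.375 | none |
| 1.2 | none | 1.5 | 1 |
| 1.5 | 1 | 1.875 | 2 |
| 1.8 | 2 | 2.25 | 3 |
| 2.1 | 3 | 2.625 | 4 |
| 2.5 | 3 | 3.125 | 4 |
| 2.6 | 4 | 3.25 | 4 |

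The lower limit is 1.5 / 1.25 = 1.2 mg/dL: below it the raised value is still ungraded. Above 2.5 the participant is already in the top grade. Between 1.2 and 2.5 the grade rises by at least one. A larger rise can also go ungraded: 1.0 to 1.4 is +40%.

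**3. ALT or AST at 3 times baseline.** Grade 1 starts at 1.1 × ULN, so a tripled value stays ungraded when baseline is below 1.1 / 3 ≈ 0.37 × ULN. The mismatch is small here, because the scale is relative to ULN.

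**4. UPCR and urine protein.** With no row in Table 5, no change in either can appear in any grade table. They remain in the by-visit summaries and listings.

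**5. What each addition would show.** A baseline-by-worst-grade shift separates the stable 1.6 from a new Grade 1. It does not show 1.0 to 1.4 (ungraded both times), a rise from 2.6 (Grade 4 both times) or any UPCR change. Only a direct count of the 7.6.1 criteria shows those.

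**6. Reference value in Part B.** The default baseline in SAP 6.1 is the last value before the first dose of IP, unless otherwise specified. SAP 6.1 also defines a pre-booster baseline, but 6.3.3 does not invoke it. Protocol Table 10 places the booster at Day 205 for recipients of three study doses, so the default value would be 205 − 1 = 204 days old at the booster. For those who had one study dose, with the booster at Day 120, it would be 119 days old. For Group B4 the booster is the first IP dose and the two baselines coincide.

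**The case against.** The strongest reply is that SAP 6.3.3 already looks at change. The sentence before the worst-grade summary plans changes from baseline at each visit by severity grade, and could be read as a per-visit grade shift. By-visit statistics include the pre-dose Day 1 value, and every result is listed, so a rise from 1.0 to 1.4 would enter those outputs. The worst-grade summary follows protocol 8.3.2, which also permits shift plots and says that clinically significant laboratory change is judged separately from the grading scale. The 7.6.1 criteria are operational triggers, not endpoints. Their clinical outcome, adjudicated biopsy-proven rejection, has its own tables, as do AESIs, which include acute kidney and liver injury. The study is descriptive, so no test or decision rule is affected.

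Most of this stands as a limit on the point. A reader might infer that the SAP has no baseline-referenced laboratory analysis; 6.3.3 does not support that.

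The remainder does not answer it. Table 5 grades values, not changes, so the change sentence cannot be programmed without a further decision. Shift plots are optional in the protocol and the SAP does not take them up for laboratory tests. The AESI definitions differ from the 7.6.1 criteria. Acute kidney injury needs a rise of 0.3 mg/dL within 48 hours, 1.5 times baseline within 7 days, or low urine volume. A rise from 1.0 to 1.4 is 1.4 times baseline, and scheduled samples on Days 1, 8 and 29 cannot date a rise to 48 hours. Acute liver injury is set against ULN, not baseline. A 7.6.1 value goes to the SRC under that criterion only if confirmed and judged suggestive of rejection, and the planned rejection tables count only adjudicated biopsy-proven events.

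**Conclusion.** The point holds as a gap in presentation for a stated secondary endpoint. Worst post-injection laboratory grade is not cross-classified by baseline grade, the change summary is worded unclearly, the Part B laboratory baseline is left to a default, and the protocol's change criteria are not counted. For creatinine, a 25% rise is invisible to grade from assumed baselines below 1.2 or above 2.5 mg/dL, and stable values of 1.5 or more are graded with no change. These limits follow from Table 5. How many participants fall in those ranges cannot be said from the documents.

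Two stronger readings should be set aside. One is that liver tests share the creatinine problem in full. They do not: they are graded relative to ULN, and the mismatch arises only below about 0.37 × ULN. The other is that graft injury would go unseen. Descriptive summaries, listings, AESI tables and adjudicated rejection all remain. What is missing is a count that separates new change from existing dysfunction. No sample size, estimate or test changes.

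**What to change.** Keep the tables now planned, and amend SAP 6.3.3 in three places.

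- **(a)** Add shifts from baseline grade to each visit and to worst post-injection grade, as 6.3.5 does for vital signs, with the pre-booster baseline for Part B.
- **(b)** Add the number and percentage of participants meeting each existing protocol 7.6.1 criterion, by organ and dose: creatinine and UPCR in kidney recipients, ALT or AST in liver recipients. State whether repeat values count. SAP 6.1 already lists kidney and liver recipients as reporting groups.
- **(c)** Reword the change-from-baseline sentence so that change is summarised as a continuous value by visit, and only observed values are graded.

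The cost is SAP wording and a few extra tables from data already scheduled for collection. The AESI and adjudicated-rejection tables stay as planned, and no clinical rule changes.
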